#### NUMBER AND TYPE OF PATIENTS:

**Accrual ceiling:** 250 for screening protocol, 18 enrolled in full protocol (to obtain 13 who complete the study)

**Abbreviated Title:** Sodium Thiosulfate (STIC)

**Version Date:** July 07, 2023

	Number	Sex	Age Range
Patients:	250	M/F	≥7 years
Volunteers:	N/A		

## Précis

Calcinosis, a serious complication of dermatomyositis, involves deposition of calcium (carbonate apatite) in soft tissue, and can result in negative impacts on quality of life and physical function. To date, there are no known effective therapies that are approved for the treatment of dermatomyositis-associated calcinosis, and there is no consensus within the medical community on the optimum treatment strategy for this often-debilitating condition.

A few reports in the literature describe treatment successes with a variety of therapeutics; however, these data are from anecdotal reports or case series and thus provide limited scientific evidence of effectiveness. Recently published reports as well as personal observations within our group have suggested that intravenous sodium thiosulfate treatment may benefit calcinosis patients. In order to gather more robust data on the utility of this medication in the treatment of calcinosis associated with adult and juvenile dermatomyositis, we propose to evaluate its effects in the context of a prospective clinical trial.

We plan to enroll participants at a single center into a single-arm, open-label study, with the overall objective of evaluating the efficacy and safety of intravenous sodium thiosulfate use in patients with moderate to severe extensive calcinosis associated with juvenile and adult dermatomyositis.

The study will enroll a maximum of 18 participants over 4 years into the full study, but up to 250 patients may screen for study entry. Eligible patients will be age 7 or older, and will have extensive calcinosis (defined as calcinosis involving the torso or 2 extremities) and moderate to severe calcinosis (indicated by a calcinosis activity visual analogue scale score of greater than or equal to 3.5 cm out of 10 cm).

Two separate evaluations performed at the NIH prior to initiation of therapy will be used as baseline data to compare in a pairwise manner to the change in assessments following treatment with sodium thiosulfate, with all other medications remaining stable. Study treatment will be 16 g/m^2 sodium thiosulfate administered 3 times weekly over a period of 10 weeks at the NIH. Subjects who complete 10 weeks of treatment or reach the primary end point by week 6 will be considered completers. Following the treatment period, all participants will return to the NIH for evaluations at weeks 24 and 62.

The primary outcome will be change in calcinosis activity visual analogue scale score from week 0 to week 10 on therapy, compared to the baseline change in calcinosis activity visual analogue scale score from week -10 to week 0 pre-treatment. Secondary measures will evaluate safety and changes in components of the Calcinosis Assessment Tool, clinical assessments of calcinosis, Mawdsley Calcinosis Questionnaire, quality of life, functional disability, muscle testing (manual and quantitative), laboratory parameters (muscle enzymes, inflammatory markers, and endothelial activation markers), gene expression, calcification pathogenesis, time to improvement, and imaging. Myositis disease activity and damage will also be assessed by validated measures.

A number of research studies will be incorporated into this clinical trial in an attempt to understand the immunologic markers associated with calcification in dermatomyositis as well as the immunologic effects of sodium thiosulfate treatment.

**Abbreviated Title:** Sodium Thiosulfate (STIC)

**Version Date:** July 07, 2023

## Abbreviations

AE	Adverse event
ACR	American College of Rheumatology
AHRP	Association of Rheumatology Health Professionals
ALT	Alanine aminotransferase
AMAT	Adult Myopathy Assessment Tool
AST	Aspartate aminotransferase
BMD	Bone mineral density
CAT	Calcinosis Assessment Tool
CCD	Charge-coupled device
CD	Clinical director
CFR	Code of Federal Regulations
CHAQ	Childhood Health Assessment Questionnaire
CHQ	Childhood Health Questionnaire
CHQ-PF50	50-Item Child Health Questionnaire – Parent Form
CK	Creatine kinase
CMAS	Childhood Myositis Assessment Score
CT	Computed tomography
CTDB	Clinical Trials Database
dbGaP	Database of Genotypes and Phenotypes
DEXA	Dual-energy x-ray absorptiometry
DLQI	Dermatology Life Quality Index
DM	Dermatomyositis (adult)
DNA	Deoxyribonucleic acid
DSMB	Data and Safety Monitoring Board
EAG	Environmental Autoimmunity Group
EMP	Endothelial microparticles
ESR	Erythrocyte sedimentation rate
FDG	Fluorodeoxyglucose
FI3	Functional Index 3
GCP	Good Clinical Practice

**Abbreviated Title:** Sodium Thiosulfate (STIC)

**Version Date:** July 07, 2023

GWAS	Genome-wide association study
HAQ	Health Assessment Questionnaire
HED	Human equivalent dose
ICH	International Conference on Harmonization
IMACS	International Myositis Assessment and Clinical Studies (Group);
IR	Infrared
IRB	Institutional Review Board
IV	Intravenous
JDM	Juvenile dermatomyositis
LD50	Lethal dose, 50%
LDH	Lactate dehydrogenase
LSCI	Laser speckle contrast imaging
MFM	Motor Function Measure in neuromuscular diseases
MMT	Manual muscle testing
MP	Microparticles
MRI	Magnetic resonance imaging
NET	Neutrophil extracellular traps
NIBIB	National Institute of Biomedical Imaging and Bioengineering
NIDDK	National Institute of Diabetes and Digestive and Kidney Diseases
NIEHS	National Institute of Environmental Health Sciences
NIH	National Institutes of Health
NIST	National Institute of Standards and Technology
OHRP	Office for Human Research Protections
OHSR	Office of Human Subjects Research
PD	Protocol deviation
PDMP	Platelet-derived microparticles
PET	Positron emission tomography
PI	Principle investigator
PROMIS	Patient Reported Outcomes Measurement Information System
PT	Prothrombin Time
PTT	Partial Thromboplastin Time
QOL	Quality of life

**Abbreviated Title:** Sodium Thiosulfate (STIC)

**Version Date:** July 07, 2023

rem	Unit of radiation (derived from Roentgen equivalent man)
RNA	Ribonucleic acid
ROM	Range of motion
SAE	Serious adverse event
SF36	36-Item Short Form Health Survey
STS	Sodium Thiosulfate
UADE	Unanticipated adverse device effect
ULN	Upper limit of normal
UP	Unanticipated problem
US	United States
VAS	Visual analogue scale
WHO	World Health Organization

**Abbreviated Title:** Sodium Thiosulfate (STIC)

**Version Date:** July 07, 2023

## 1. Background

Juvenile and adult dermatomyositis (JDM, DM respectively) are inflammatory muscle diseases that can also have protean non-muscular manifestations. One such non-muscle complication is calcinosis, which is the development of dystrophic soft tissue calcification. This complication is more common in pediatric patients with JDM than adults, with calcinosis occurring in up to 35% of JDM patients and up to 20% of adult DM patients. Spontaneous resolution of cutaneous calcification is rare, treatment remains a challenge, and calcinosis has been associated with decreased physical function and poor outcomes (1). Thus, it is critical to identify and develop effective treatment options for patients experiencing this comorbid condition.

## 1.2. Non-Clinical Toxicology and Pharmacology of Sodium Thiosulfate

Non-clinical toxicology and pharmacology data has been provided to NIEHS by Hope Pharmaceuticals (the supplier of investigational product), including information that has been submitted to FDA as part of the initial IND on file (NDA #201,444). This data is summarized below.

### Single Dose Toxicity

The sodium thiosulfate material safety data sheet (MSDS) provided by Hope Pharmaceuticals (supplier of the investigational product) provides information about the intravenous dose required to kill 50% of a test animal population ( $LD_{50}$ ) for several species (15). This data is summarized in Table 1 in relation to its human equivalent dose (HED), which was estimated in accordance with Center for Drug Evaluation and Research (CDER) guidance (16).

**Abbreviated Title:** Sodium Thiosulfate (STIC)

**Version Date:** July 07, 2023

**Table 1 LD50 Values for STS Administered Intravenously in Relation to HED**

Species	LD 50 (mg/kg)	HED a (mg/kg)
Rat	>2,500	>403
Mouse	1190	97
Dog	3000	1667

aHED assumes a 60 kg adult and was derived by dividing the rat dose by 6.2, mouse dose by 12.3, and dog dose by 1.8

As dog is the species most comparable in size to a human and has been used in animal experiments of calcinosis, it is considered the most relevant species for a human safety comparison in this instance (17). The proposed sodium thiosulfate dose in this study is 16 g/m^2 3 times weekly for 10 weeks. Assuming a 60 kg adult, as used for the HED in table 1, would have a body surface area of 1.13 m^2 they would be receiving in our study a dose of 18.08 grams at each infusion, which would come to 301.3 mg/kg body weight. This is well below the HED of the LD50 for rats and dogs as noted in Table 1. It is important to note that, as described in Section 1.3, sodium thiosulfate has been administered to humans in clinical trial settings in combination with chemotherapeutic agents to decrease toxicity and for the treatment of vascular calcification in end stage renal disease (ESRD) using intravenous doses as high as 25 g/m^2 3x/week for up to 5 months in adults and up to 20 g/m^2 in children in frequencies up to 3 times weekly.

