### 1.3. Sodium Thiosulfate Use in Humans

Sodium thiosulfate (used in conjunction with sodium nitrite) is currently approved by the FDA for the treatment of cyanide poisoning at a dose of 12.5 g in adults and 0.25 g/kg in children (not to exceed 12.5 g) (24). This dose can be repeated at half of the original dose if needed, leading to a total dose of 18.75 g. It is administered via intravenous infusion of a sodium thiosulfate injection solution containing 12.5 g/50 mL, at a rate of 0.625 to 1.25 g/min (approximately 10-20 minutes).

There are no clinical trials to date that have evaluated the safety of intravenous administration of sodium thiosulfate in humans for the treatment of juvenile and adult dermatomyositis. George Washington University is currently evaluating the topical use of sodium thiosulfate in combination with fractional carbon dioxide laser in the treatment of dermatomyositis associated calcinosis (ClinicalTrials.gov Identifier: NCT01572844). Additional human experience with this drug across other indications is extensive. The numerous reports available in the literature span several decades, with several describing longer-term and repeat-dose use of sodium thiosulfate in humans. For example, a 1985 publication by Yatzidis (13), who was evaluating it as a treatment for recurrent calcium urolithiasis, reported the administration of 20 mmol sodium thiosulfate daily (~5 g/day, or ~3 g/m^2/day for an average adult) over the course of 4 years in a cohort of 34 patients (overall, the group had a decline in new stone development during the sodium thiosulfate treatment period).

Table 2 summarizes clinical studies identified as of 08 June 2015 (through a PubMed and clinicaltrials.gov search) that have been conducted with sodium thiosulfate via the intravenous (IV) route and associated dose levels as available.

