### **12.3. Justification for Selection of Dose and Frequency of Sodium Thiosulfate**

We have chosen a dose of 16 g/m^2 for this study. Based on the previously done human studies and existing animal data this dose should be able to be administered without serious adverse events. Based on cases we have accumulated this appears to be a dose where patients tend to respond, with poor response to low dose treatment. Based on the case reports we have accumulated this appears to be the minimal dose with a significant beneficial effect. With the published side effect data, there is also a trend towards greater electrolyte abnormalities at larger doses so we tried to keep dosing below 20 g/m^2.

We would like to maximize drug frequency in order to minimize the time it takes patients to get all of their infusions. In a study of sodium thiosulfate for cisplatin toxicity patients received medication 3 times a week with minimal side effects except for nausea (NCT00716976 unpublished data). They noted that some electrolyte abnormalities in these patients could persist for 24 hours, but very rarely beyond that. Based on this there is a concern that infusions more frequent than three times a week will not give patients enough time to completely correct any transient hypernatremia or hypocalcemia and thus they could accumulate a larger change eventually becoming clinically dangerous. In those patients who had electrolyte abnormalities beyond 24 hours it was often elevated phosphorus. We will monitor patients for this and in those with elevated phosphorus we will initiate sevelamer to reduce their phosphorus. In the cases, we have heard those patients who were on twice a week dosing tended to have stabilization of their calcinosis, but not improvement so we felt there was a need for at least three times a week infusions.

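### Does the unsourced body surface area of 1.13 m² in Section 1.2 undermine the animal safety comparison for the study dose?

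*Combined protocol and SAP*

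**What the plan says.** Section 1.2 (Single Dose Toxicity, Table 1) lists intravenous LD50 values and their HEDs for a 60 kg adult: rat >403 mg/kg, mouse 97 mg/kg, dog 1667 mg/kg. Of the dog it says that "it is considered the most relevant species for a human safety comparison in this instance".

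The text below the table converts 16 g/m² for that adult: "Assuming a 60 kg adult, as used for the HED in table 1, would have a body surface area of 1.13" m², so that "they would be receiving in our study a dose of 18.08 grams at each infusion, which would come to 301.3 mg/kg body weight". It concludes: "This is well below the HED of the" LD50 for rats and dogs. The mouse is not mentioned in that sentence. The paragraph then turns to human exposure, citing intravenous doses up to 25 g/m² three times weekly for up to 5 months in adults and up to 20 g/m² in children.

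Section 1.3, describing a kidney-stone study that gave 20 mmol daily, restates the dose as approximately "5 g/day, or ~3 g/m 2 /day for an average adult". Section 12.3 justifies the dose in general terms: "Based on the previously done human studies and existing animal data this dose should be able to be administered without serious adverse events".

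**The concern.** The area of 1.13 m² comes with no formula, height or citation, and it sits badly with the next section. Dividing about 5 g by about 3 g/m² gives an average adult of about 1.67 m². At 1.13 m², the same 5 g would be 4.4 g/m². If 1.13 m² is too small for 60 kg, the mg/kg figure is too low and the margins against the animal values are flattered. The rat margin is the exposed one, because 301.3 mg/kg is already 75% of the rat figure.

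In the supplied text this is the only place where the study dose is set against an animal number, and Section 12.3 counts animal data among its grounds for the dose. What would be at stake is a safety statement, in a trial that enrols children, that its own inputs do not support.

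**Working it through.** **Reproducing the printed figures.** Inputs are from Section 1.2 and Table 1.

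- Dose: 16 g/m² × 1.13 m² = 18.08 g; 18,080 mg / 60 kg = 301.3 mg/kg.
- HEDs: rat 2500/6.2 = 403; mouse 1190/12.3 = 97; dog 3000/1.8 = 1667.

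All agree with the text. There is no arithmetic slip; only the area is in question.

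**Area implied by Section 1.3.** 5/3 = 1.67 m². Both inputs are marked approximate, so rounding alone allows 4.5/3.5 = 1.29 to 5.5/2.5 = 2.20 m². The average adult's weight is not stated. To carry the area to 60 kg I assume a weight W of 60 to 80 kg and area proportional to weight^(2/3): area at 60 kg = 1.67 × (60/W)^(2/3).

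**Dose in mg/kg at 60 kg** = 16,000 × area / 60.

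| Area at 60 kg (m²) | Basis | g | mg/kg | % of rat 403 | % of dog 1667 |
|---|---|---|---|---|---|
| 1.13 | Section 1.2 as printed | 18.08 | 301.3 | 75 | 18 |
| 1.06 | 1.29 m², W = 80 kg | 17.0 | 283 | 70 | 17 |
| 1.29 | rounding low end, W = 60 kg | 20.6 | 343 | 85 | 21 |
| 1.38 | 1.67 m², W = 80 kg | 22.0 | 367 | 91 | 22 |
| 1.50 | 1.67 m², W = 70 kg | 24.1 | 401 | 99 | 24 |
| 1.67 | 1.67 m², W = 60 kg | 26.7 | 444 | 110 | 27 |
| 2.20 | rounding high end, W = 60 kg | 35.2 | 587 | 146 | 35 |

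**Where each comparison would turn.** The area at which the dose equals an HED is HED × 60 / 16,000.

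- Rat: 403 × 60 / 16,000 = 1.51 m². This lies inside the plausible range, so the rat comparison is sensitive to the input.
- Dog: 1667 × 60 / 16,000 = 6.25 m², far above any area considered.
- Mouse: 97 × 60 / 16,000 = 0.36 m². The mouse figure is exceeded at every area in the table, including the printed one (301.3/97 = 3.1 times), so the area does not affect that comparison.

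**Is it a contradiction?** On the central reading of Section 1.3, 1.13 m² is low. With 1.67 m² taken at face value, the average adult would have to weigh about 107 kg for a 60 kg adult to have 1.13 m² (60 × (1.67/1.13)^1.5, unrounded inputs). But the low end of the rounding range, scaled from 80 kg, gives 1.06 m², or 1.11 m² with weight^(1/2). Both are below 1.13 m². That is an extreme corner, but it means the documents alone do not exclude the printed value.

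**What depends on the conversion.** Section 12.2 doses each infusion per m², so each participant's own area is used. The human-exposure comparison is also in g/m²: 16/25 = 64% of the highest adult dose cited and 16/20 = 80% of the highest paediatric dose cited. Neither step uses 1.13 m².

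**The case for a change.** The best case for a correction is that the edit is cheap and the sentence is one that safety reviewers may read. The area is unsourced. Across average-adult weights of 60 to 80 kg at the central 1.67 m², the dose is 91% to 110% of the rat figure, which nobody would call well below. The sentence also passes over the mouse, the one species in Table 1 whose HED the printed dose exceeds, and that omission needs no assumption about area.

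Much of this stands as description. The value is unsupported, it is low on the central reading, and a clear rat margin is not shown.

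The step to a needed change does not stand. The rat entry is a lower bound (>403), so even 444 mg/kg would not show the dose to be above the rat HED. The 110% figure requires an average adult of exactly 60 kg. The mouse value is printed in Table 1 for any reader to see, the concluding sentence claims only rats and dogs, and the text gives its reason for relying on the dog. Section 12.3 puts human studies beside animal data, adds accumulated cases and published side-effect data, and does not use the 301.3 mg/kg figure. Participants are protected by the hourly calcium and sodium checks in the first two adults (Section 3.1) and by the independent monitoring board (Section 14.1), neither of which rests on the rat comparison.

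**Conclusion.** No change to the plan follows. Section 1.2 contains an unsourced and probably low illustrative input, which makes the rat half of one background sentence stronger than the documents can show: 75% of the rat bound as printed, against about 91% to 110% if 1.67 m² belongs to an adult of 60 to 80 kg and area scales with weight^(2/3). The dog half holds throughout, at 17% to 35% of the dog HED over the areas tabulated. No infusion, eligibility rule, endpoint, sample size or analysis uses the figure, and the human-exposure argument bypasses it. Correcting it would tidy the background without altering any decision in the trial. This reading rests on the rounding and scaling assumptions shown above, and it takes no position on the dose itself.

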### **Repeated Dose Toxicity**

Rats were administered 125 mg/kg intramuscular for 4 weeks or 3 months. Changes in the capillary walls of the thyroid and adrenal cortex were visible at 4 weeks. The vessels were dilated and exhibited a lowered alkaline phosphatase activity. After 3 months, the vessels of the kidneys displayed clear changes, including atrophy of the glomeruli and dilation of the glomerular capillaries, which were permeable to plasma. An increased permeability of liver capillary walls and an increase in Kupffer cells were also noted (18).

### **Genotoxicity**

A study published by the U.S. Food and Drug Administration reports that sodium thiosulfate tested negative for mutagenic potential in the bacterial reverse mutation assay (Ames test) using *S. typhimurium* strains TA98, TA100, TA1535, TA1537, TA1538, and *E. coli* strain WP2 ( $\pm$  S9 metabolic activation) (19).

### **Carcinogenicity**

Long-term studies in animals have not been performed to evaluate the potential carcinogenicity of sodium thiosulfate.

### **Reproductive Toxicity**

Reproductive toxicity data is from unpublished data from original IND submission for sodium thiosulfate. Pregnant mice (N=20-22/group) were administered sodium thiosulfate via oral gavage at doses of 0, 5.5, 25.5, 118 or 550 mg/kg from day 6 through day 15 of gestation. On day 17 all dams were subjected to caesarean section and the number of implantation sites, resorption sites, and live and dead fetuses were recorded. The body weights of the live pups were recorded. All fetuses were examined grossly for the presence of external congenital abnormalities. One-third of the fetuses of each litter underwent detailed visceral examinations. The remaining two-thirds were stained with

**Abbreviated Title:** Sodium Thiosulfate (STIC)

**Version Date:** July 07, 2023

alizarin red S dye and examined for skeletal defects. Sodium thiosulfate was not found to be embryotoxic or teratogenic in this study.

Pregnant rats (N=20-22/group) were administered sodium thiosulfate via oral gavage at doses of 0, 4, 19, 86 or 400 mg/kg from day 6 through day 15 of gestation. On day 20 all dams were subjected to caesarean section and the number of implantation sites, resorption sites, and live and dead fetuses were recorded. The body weights of the live pups were recorded. All fetuses were examined grossly for the presence of external congenital abnormalities. One-third of the fetuses of each litter underwent detailed visceral examinations. The remaining two-thirds were stained with alizarin red S dye and examined for skeletal defects. Sodium thiosulfate was not found to be embryotoxic or teratogenic in this study.

Pregnant hamsters (N=20-22/group) were administered sodium thiosulfate via oral gavage 0, 4, 19, 86 or 400 mg/kg from day 6 through day 10 of gestation. On day 14, all dams were subjected to caesarean section and the number of implantation sites, resorption sites, and live and dead fetuses were recorded. The body weights of the live pups were recorded. All fetuses were examined grossly for the presence of external congenital abnormalities. One-third of the fetuses of each litter underwent detailed visceral examinations. The remaining two-thirds were stained with alizarin red S dye and examined for skeletal defects. Sodium thiosulfate was not found to be embryotoxic or teratogenic in this study.

## **Pharmacology**

Sodium thiosulfate has been shown both *in vitro* and *in vivo* studies to reduce calcification of a variety of tissues in a number of animal models.

In an *in vitro* model, 3T3-L1 preadipocytes were induced into mature adipocytes (20). The mature adipocytes underwent calcification after being treated with high phosphorus media leading to increased expression of osteopontin and the osteoblast transcription factor Runx2 and decreased expression of adipocyte transcription factors peroxisome proliferator-activated receptor  $\gamma$  (PPAR $\gamma$ ) and CCAAT-enhancer-binding protein  $\alpha$  (CEBP $\alpha$ ). When the mature adipocytes were exposed to sodium thiosulfate, calcification was inhibited in a dose dependent manner and the secretion of leptin and vascular endothelial growth factor (VEGF) from adipocytes was also decreased.

The effectiveness of sodium thiosulfate was investigated in a Wistar albino rat model that were bilaterally myringotomized, thus inducing myringosclerosis (MS, calcification of the tissues of the middle ear) around the handle of the malleus and near the annular region (21). Thirty rats were administered topical sodium thiosulfate or saline daily in the right ear. The left ear of all rats was left untreated to serve as the control. It was observed that rats who received sodium thiosulfate showed reduced calcium deposition and less formation of MS ( $p < .05$ ).

Sodium thiosulfate was administered to uremic rats to determine if it could prevent the development of vascular calcifications in chronic kidney disease (22). The uremic rats treated with sodium thiosulfate had no histological evidence of calcification in the aortic wall in comparison to the control group (untreated rats) in which three-fourths showed aortic calcification. In those rats receiving sodium thiosulfate, urine calcium excretion was elevated and the calcium content of aorta, heart, and renal tissues was significantly reduced in comparison to the control animals. Sodium thiosulfate also lowered plasma

**Abbreviated Title:** Sodium Thiosulfate (STIC)

**Version Date:** July 07, 2023

ionized calcium, induced metabolic acidosis and lowered bone strength in relation to the control group.

Sodium thiosulfate orally has also been shown to reduce the formation of calcium kidney stones in an uncontrolled clinical trial (23). To examine this further, genetic hypercalciuric rats, an animal model of calcium phosphate stone formation, were fed normal food either with or without sodium thiosulfate for 18 weeks. Urine chemistries, supersaturation, and the upper limit of metastability of urine were assessed. Eleven of the 12 untreated rats formed stones compared to three of the 12 sodium thiosulfate-treated rats ( $P < 0.002$ ). Urine calcium and phosphorus levels were higher in rats receiving sodium thiosulfate in the feed. Urine citrate, urine volume and urine pH were lower in the sodium thiosulfate-treated rats. Overall, the administration of sodium thiosulfate reduced the calcium phosphate stone formation in this rat model.

The above data show the promise of sodium thiosulfate administration to reduce calcification. Based upon these results, a clinical trial is needed to test the potential efficacy and safety of sodium thiosulfate administration for the treatment of juvenile and adult dermatomyositis.

